2.2 APR-246

[figure not shown]

Figure

2.3 APR-246 Preclinical Studies

2.3.1 Pharmacology and Mode of Action

2.3.2 Safety Pharmacology

A thick black horizontal bar, likely a redacted section of text.

[figure not shown]
2.3.3 Pharmacokinetics and Metabolism in Animals

A horizontal bar chart consisting of six solid black bars of increasing height from left to right. The bars are separated by small gaps and are set against a white background. The heights of the bars correspond to the values in the following data table.

A series of six horizontal black bars of varying lengths, decreasing in length from left to right. The bars are positioned in a horizontal line, with the first bar being the longest and the sixth bar being the shortest.

2.3.4 Toxicology

© 2019 Pearson Education, Inc.

In

[figure not shown]
■ ■ ■ 246 Clinical Studies

2.4.1 Phase 1/2 Study in Solid and Hematological Malignancies

The image consists of a series of horizontal black bars of varying lengths and positions, suggesting a redacted document. The bars are arranged in three distinct groups. The top group contains several bars of moderate length, with one bar on the far right being significantly shorter. The middle group contains a single, very long bar that spans most of the width of the frame. The bottom group contains a single, very long bar that spans most of the width of the frame. The bars are set against a white background.

2.4.2 Phase 1/1b Study in Refractory Hematologic Malignancies

A series of horizontal black bars of varying lengths, with a few white bars interspersed, arranged in a grid pattern. The bars are positioned in a staggered, non-overlapping manner across the frame. The lengths of the bars vary significantly, with some being very short and others being quite long. The white bars are located at the top, bottom, and in the middle of the grid, creating a pattern of black and white horizontal stripes.

A thick black horizontal bar is positioned at the bottom of the page, spanning most of the width of the text area. It is likely a decorative element or a redacted section of the document.

A series of horizontal black bars of varying lengths, with the longest bar at the bottom.

2.4.6 Phase 1 Study in Combination with Venetoclax and Azacitidine in *TP53*-Mutant Myeloid Neoplasms

A series of horizontal black bars of varying lengths, likely representing redacted text or data. The bars are arranged vertically, with some shorter bars at the top and longer ones below, creating a stepped effect.

2.4.7 APR-246 CNS Safety Overview

A series of horizontal black bars of varying lengths. The longest bar is at the bottom, followed by a shorter bar near the top left, and several very short bars near the top center.

[figure not shown]
[figure not shown]
[figure not shown]
[figure not shown]
[figure not shown]
[figure not shown]
[figure not shown]
[figure not shown]
[figure not shown]
[figure not shown]
[figure not shown]
[figure not shown]
[figure not shown]
2.4.8 APR-246 Cardiac Safety Overview

A large number of horizontal black bars of varying lengths, likely representing data points or items in a list. The bars are arranged in a grid-like pattern, with some bars being significantly longer than others, suggesting a distribution or a list of items with varying magnitudes or frequencies.

246 Pharmacokinetics in Humans

Table 1. Average Exposure After Infusion of a Fixed Dose of 4.5 g of APR-246 for 6 hours in Males and Females

		Males	Females
1	2	3	4
5	6	7	8
9	10	11	12
13	14	15	16
17	18	19	20
21	22	23	24
25	26	27	28
29	30	31	32
33	34	35	36
37	38	39	40
41	42	43	44
45	46	47	48
49	50	51	52
53	54	55	56
57	58	59	60
61	62	63	64
65	66	67	68
69	70	71	72
73	74	75	76
77	78	79	80
81	82	83	84
85	86	87	88
89	90	91	92
93	94	95	96
97	98	99	100
101	102	103	104
105	106	107	108
109	110	111	112
113	114	115	116
117	118	119	120
121	122	123	124
125	126	127	128
129	130	131	132
133	134	135	136
137	138	139	140
141	142	143	144
145	146	147	148
149	150	151	152
153	154	155	156
157	158	159	160
161	162	163	164
165	166	167	168
169	170	171	172
173	174	175	176
177	178	179	180
181	182	183	184
185	186	187	188
189	190	191	192
193	194	195	196
197	198	199	200
201	202	203	204
205	206	207	208
209	210	211	212
213	214	215	216
217	218	219	220
221	222	223	224
225	226	227	228
229	230	231	232
233	234	235	236
237	238	239	240
241	242	243	244
245	246	247	248
249	250	251	252
253	254	255	256
257	258	259	260
261	262	263	264
265	266	267	268
269	270	271	272
273	274	275	276
277	278	279	280
281	282	283	284
285	286	287	288
289	290	291	292
293	294	295	296
297	298	299	300
301	302	303	304
305	306	307	308
309	310	311	312
313	314	315	316
317	318	319	320
321	322	323	324
325	326	327	328
329	330	331	332
333	334	335	336
337	338	339	340
341	342	343	344
345	346	347	348
349	350	351	352
353	354	355	356
357	358	359	360
361	362	363	364
365	366	367	368
369	370	371	372
373	374	375	376
377	378	379	380
381	382	383	384
385	386	387	388
389	390	391	392
393	394	395	396
397	398	399	400
401	402	403	404
405	406	407	408
409	410	411	412
413	414	415	416
417	418	419	420
421	422	423	424
425	426	427	428
429	430	431	432
433	434	435	436
437	438	439	440
441	442	443	444
445	446	447	448
449	450	451	452
453	454	455	456
457	458	459	460
461	462	463	464
465	466	467	468
469	470	471	472
473	474	475	476
477	478	479	480
481	482	483	484
485	486	487	488
489	490	491	492
493	494	495	496
497	498	499	500
501	502	503	504
505	506	507	508
509	510	511	512
513	514	515	516
517	518	519	520
521	522	523	524
525	526	527	528
529	530	531	532
533	534	535	536
537	538	539	540
541	542	543	544
545	546	547	548
549	550	551	552
553	554	555	556
557	558	559	560
561	562	563	564
565	566	567	568
569	570	571	572
573	574	575	576
577	578	579	580
581	582	583	584
585	586	587	588
589	590	591	592
593	594	595	596
597	598	599	600
601	602	603	604
605	606	607	608
609	610	611	612
613	614	615	616
617	618	619	620
621	622	623	624
625	626	627	628
629	630	631	632
633	634	635	636
637	638	639	640
641	642	643	644
645	646	647	648
649	650	651	652
653	654	655	656
657	658	659	660
661	662	663	664
665	666	667	668
669	670	671	672
673	674	675	676
677	678	679	680
681	682	683	684
685	686	687	688
689	690	691	692
693	694	695	696
697	698	699	700
701	702	703	704
705	706	707	708
709	710	711	712
713	714	715	716
717	718	719	720
721	722	723	724
725	726	727	728
729	730	731	732
733	734	735	736
737	738	739	740
741	742	743	744
745	746	747	748
749	750	751	752
753	754	755	756
757	758	759	760
761	762	763	764
765	766	767	768
769	770	771	772
773	774	775	776
777	778	779	780
781	782	783	784
785	786	787	788
789	790	791	792
793	794	795	796
797	798	799	800
801	802	803	804
805	806	807	808
809	810	811	812
813	814	815	816
817	818	819	820
821	822	823	824
825	826	827	828
829	830	831	832
833	834	835	836
837	838	839	840
841	842	843	844
845	846	847	848
849	850	851	852
853	854	855	856
857	858	859	860
861	862	863	864
865	866	867	868
869	870	871	872
873	874	875	876
877	878	879	880
881	882	883	884
885	886	887	888
889	890	891	892
893	894	895	896
897	898	899	900
901	902	903	904
905	906	907	908
909	910	911	912
913	914	915	916
917	918	919	920
921	922	923	924
925	926	927	928
929	930	931	932
933	934	935	936
937	938	939	940
941	942	943	944
945	946	947	948
949	950	951	952
953	954	955	956
957	958	959	960
961	962	963	964
965	966	967	968
969	970	971	972
973	974	975	976
977	978	979	980
981	982	983	984
985	986	987	988
989	990	991	992
993	994	995	996
997	998	999	1000

2.5 Venetoclax

Venetoclax is a Bcl-2 inhibitor that was approved by the U.S. FDA for the treatment of adult patients with CLL or small lymphocytic lymphoma in the front line and relapsed/refractory settings.

In the phase 3 study comparing venetoclax plus rituximab with bendamustine plus rituximab in relapsed and/or refractory CLL (MURANO), the 2-year rates of progression-free survival (PFS) were significantly higher in the venetoclax-rituximab group (84.9%) than in the bendamustine-rituximab group (36.3%)⁴⁶. The benefit was maintained across all clinical and biologic sub-groups, including the sub-group of patients with chromosome 17p deletion, where the 2-year rate of PFS among patients with chromosome 17p deletion was 81.5% in the venetoclax-rituximab group versus 27.8% in the bendamustine-rituximab group (hazard ratio, 0.13; 95% CI, 0.05 to 0.29).

The most common adverse reactions ($\geq 20\%$) of any grade in patients receiving venetoclax monotherapy are neutropenia, diarrhea, nausea, anemia, upper respiratory tract infection, thrombocytopenia, and fatigue. Serious adverse reactions were reported in 43.8% of patients. The most frequent serious adverse reactions ($\geq 2\%$) were pneumonia, febrile neutropenia, pyrexia, autoimmune hemolytic anemia (AIHA), anemia, and tumor lysis syndrome (TLS). More detailed information about the safety profile of venetoclax in combination with rituximab may be found in the United States prescribing information (USPI) for venetoclax⁴⁷.

Following multiple doses under fed conditions, C_{max} of venetoclax is reached 5 – 8 hours after dose. It is recommended that venetoclax be administered with a meal as food increases the absorption after oral administration. Venetoclax is cleared from systemic circulation via hepatic elimination. The $T_{1/2}$ is approximately 26 hours. The PK of venetoclax does not change over time. Venetoclax is predominantly metabolized by CYP3A4/5. CYP3A4 inhibitors and inducers as well as P-gp inhibitors cause clinically relevant drug-drug interactions with venetoclax. For the same reason certain food must be avoided: grapefruit, grapefruit juice, Seville oranges (often used in marmalades), starfruit (CYP3A inhibiting), and St John's wort (CYP3A inducing). Based on their metabolic profiles, a PK drug-drug interaction of venetoclax with APR-246 is considered unlikely.

2.6 Rituximab

Rituximab is a monoclonal antibody that targets the CD20 antigen expressed on the surface of pre-B and mature B-lymphocytes. Upon binding to CD20, rituximab mediates B-cell lysis. Possible mechanisms of cell lysis include complement dependent cytotoxicity and antibody dependent cell mediated cytotoxicity. B cells are believed to play a role in the pathogenesis of rheumatoid arthritis and associated chronic synovitis. In this setting, B cells may be acting at multiple sites in the autoimmune/inflammatory process, including through production of rheumatoid factor and other autoantibodies, antigen presentation, T-cell activation, and/or proinflammatory cytokine production.

In NHL patients, administration of rituximab resulted in depletion of circulating and tissue-based B cells. Among 166 patients in NHL Study 1 (NCT000168740), circulating CD19-positive B cells were depleted within the first three weeks with sustained depletion for up to 6 to 9 months post treatment in 83% of patients. B-cell recovery began at approximately 6 months and median B-cell levels returned to normal by 12 months following completion of treatment. There were sustained and statistically significant reductions in both IgM and IgG serum levels observed from 5 through 11 months following rituximab administration; 14% of patients had IgM and/or IgG serum levels below the normal range⁴⁸.

The PK was characterized in 203 NHL patients receiving 375 mg/m² rituximab weekly by IV infusion for 4 doses. Rituximab was detectable in the serum of patients 3 to 6 months after completion of

treatment. Based on a population PK (popPK) analysis of data from 298 NHL patients who received rituximab once weekly or once every three weeks, the estimated median $T_{1/2}$ was 22 days (range, 6.1 to 52 days). Patients with higher CD19-positive cell counts or larger measurable tumor lesions at pretreatment had a higher CL. However, dose adjustment for pretreatment CD19 count or size of tumor lesion is not necessary. Age and gender had no effect on the PK of rituximab⁴⁸.

As rituximab is a monoclonal antibody, no PK drug-drug interaction is expected with APR-246.

2.7 Rationale for Combinations of APR-246 with Venetoclax + Rituximab

[REDACTED]

2.8 Rationale for Dose of APR-246 in Combination with Venetoclax and Rituximab

[REDACTED]

[REDACTED]

[REDACTED]

venetoclax and rituximab.

2.9 Rationale for Oral Dose of APR-246 in the Monotherapy Cycle

Term	Percentage
GMOs	75
Organic	95
Natural	90
Artificial	25

2.10 Potential Risks and Benefits

2.10.1 Potential Risks

A horizontal bar chart with 10 categories on the y-axis and a count of samples on the x-axis (0 to 1000). Category 1 has the highest count (approx. 900), while categories 2, 3, 4, 5, 6, 7, 8, 9, and 10 have lower counts (approx. 100-200).

Category	Count
1	~900
2	~150
3	~150
4	~150
5	~150
6	~150
7	~150
8	~150
9	~150
10	~150

A large block of black redacted text, consisting of approximately 20 lines of text, rendered as a solid black rectangle. The text is completely obscured and cannot be read.

2.10.2 Potential Benefits

The purpose of this clinical trial is to define the PD, safety and tolerability of APR-246 in combination with venetoclax and rituximab in patients with RT and to determine preliminary efficacy. Considering the lack of effective treatment options in these patients, the benefit/risk assessment supports the use of APR-246 in this trial.

2.11 Characteristics of a Well-Conducted Trial

The following characteristics of an adequate and well-conducted trial will be implemented:

1. The Investigators will be well qualified by scientific training and experience.
2. Detailed electronic Case Report Forms (eCRFs) will be completed for every patient.
3. Requirements for institutional ethics review as set forth by the appropriate Institutional Review Board/Independent Ethics Committee (IRB/IEC), Title 21 Code of Federal Regulations (CFR) Part 56, the European Union Directive 2001/20/EU and its associated Detailed Guidances, European Union Good Clinical Practice (GCP) Directive 2005/28/EC, the International Council for Harmonization (ICH) Guideline for GCP, Sections 3 and 4, and the terms of the Declaration of Helsinki (2013), will be followed.
4. Requirements for informed consent in accordance with institutional guidelines, FDA requirements as specified in Title 21 CFR, Part 50, the European Union Directive 2001/20/EC and its associated Detailed Guidances, European Union GCP Directive 2005/28/EC, the ICH Guideline for GCP, Section 4.8, and the terms of the Declaration of Helsinki (2013), will be followed.
5. Safety data will be recorded and evaluated.
6. Routine monitoring visits will be conducted by the Sponsor's representative to ensure data accuracy.
7. Drug accountability will be strictly maintained.
8. This trial will be conducted according to GCP, the protocol and applicable regulatory requirements.

2.12 Patient Population

This study will enroll adult male and female patients of ≥ 18 years of age with documented histologic diagnosis of RT by WHO criteria who have relapsed and/or refractory disease following at least one line of prior therapy for RT.

3.0 TRIAL OBJECTIVES AND PURPOSE

3.1 Primary Objective

To evaluate the PD, safety and tolerability of APR-246 administered IV in combination with venetoclax and rituximab in patients with RT to determine the recommended dose of APR-246.

3.2 Secondary Objectives

1. To investigate a pharmacologically active dose of APR-246 by using PD markers of APR-246 activity,

including in peripheral blood malignant cells, using flow cytometry and other techniques.

2. To investigate PD markers of APR-246 activity in monotherapy, including in peripheral blood malignant cells, using flow cytometry and other techniques (*PK/PD Substudy of APR-246 Monotherapy*).
3. To determine the PK profile of APR-246.
4. To investigate the PK of APR-246 administered PO (*PK/PD Substudy of APR-246 Monotherapy*).
5. To assess preliminary clinical activity of APR-246 in combination with venetoclax and rituximab therapy.

3.3 Exploratory Objectives

To explore the exposure response relationship of APR-246 with safety and/or efficacy when combined with venetoclax and rituximab therapy.

4.0 TRIAL DESIGN

4.1 Overview of Trial Design

Treatment will be administered on an outpatient basis but may be administered in the inpatient setting for patients who are hospitalized and meet criteria for study enrollment. No investigational or commercial agents or therapies other than those described below may be administered with the intent to treat the patient's disease under study.

Monotherapy Cycle

There is a 7-day monotherapy cycle where patients receive APR-246 IV on Day 1 and APR-246 PO on Day 2. The primary purpose of the monotherapy cycle is to obtain peripheral blood for monotherapy PK and PD analyses following IV and PO administration of APR-246.

Patients will start treatment with APR-246 IV as a single agent administered on Day 1 of a single 7-day monotherapy cycle at the assigned cohort dose level, prior to Cycle 1 Day 1 of combination therapy. On Day 2 of the 7-day monotherapy lead-in period, patients will receive a single dose of APR-246 administered PO at the dose of 500 mg. After review of oral PK data from at least 6 patients, a decision can be made whether to increase the PO dose of APR-246 and/or administer APR-246 with a standard high-fat meal to investigate, respectively, dose linearity in PK and/or the effect of food on oral absorption of APR-246. Dose escalation of the oral dose or switching to administration with food will be determined by PK to ensure that the APR-246 exposure levels after oral dosing do not exceed the exposure levels after IV administration in terms of C_{max} and AUC.

Combination Treatment

After the APR-246 monotherapy lead-in, study treatment will consist of APR-246 administered as an IV infusion at the same assigned dose that was used during the monotherapy lead-in period once weekly, on Days 1, 8 and 15 of each cycle, concurrently with venetoclax for the 5-week ramp-up at the dose of 20 mg during Week 1, 50 mg during Week 2, 100 mg during Week 3, 200 mg during Week 4, and 400 mg during Week 5. Beginning Cycle 2 Day 1, venetoclax will be administered at 400 mg (or tolerable dose following 5-week ramp up) PO daily. IV rituximab will be initiated at 375 mg/m² on Cycle 2, Day 2 and then administered at 500 mg/m² on Day 2 of Cycles 3-7. After 6 cycles of treatment with APR-246 in combination with venetoclax + rituximab, APR-246 + venetoclax will continue to be

administered starting at Cycle 8 for up to a total of 24 cycles. Cycle 1 will consist of 35 days. Cycles 2 and beyond will be 28 days. The safety assessment (DLT) period begins at the start of treatment and extends to the end of Cycle 3.

Patients with RT will receive APR-246 administered IV at the assigned cohort dose with standard doses of venetoclax and rituximab. Dose escalation will proceed in a standard 3 + 3 dose escalation design.

The intended three dose levels of APR-246 are: 1.5 g/day, 3.0 g/day, and 4.0 g/day administered as an IV infusion over 6 hours. The dose escalation will proceed until a pharmacologically active dose level is achieved. It will be stopped if the maximum tolerated dose (MTD) is reached at a dose level below the maximum planned dose of 4.0 g/day. For the determination of MTD the following rules will be applied:

- Three patients will be enrolled to Dose Level 1.
- If 0 patients out of 3 experience a DLT at Dose Level 1 (1.5 g/day of APR-246), the dose will advance to the next level (Dose Level 2, 3.0 g/day).
- If 1 of the first 3 patients at Dose Level 1 experiences a DLT, 3 additional patients will be recruited and treated at the same dose level (1.5 g/day of APR 246).
- If ≥ 2 patients out of 3-6 patients in a cohort experience a DLT at Dose Level 1 (1.5 g/day of APR-246), the study will temporarily discontinue enrollment and the Data Review Team (DRT) will consider further enrollment and possible dose/schedule adjustments.
- If < 2 patients out of 6 experiences a DLT at Dose Level 1 (1.5 g/day), dose escalation will proceed to the next cohort level (Dose Level 2, 3.0 g/day).
- For each cohort, if there are 0 DLTs in the first 3 patients enrolled, the cohort will advance to the next level. If there is 1 DLT in the first 3 patients enrolled to a cohort, the cohort will enroll an additional 3 patients. If there are ≥ 2 DLTs in a cohort, the prior lower dose level will be declared the MTD.
- If there are ≤ 1 DLT in the first 3 patients enrolled at Dose Level 3, 4.0 g/day APR-246, the study will enroll 3 additional patients at Dose Level 3. If there are ≤ 1 DLTs in 6 patients enrolled at Dose Level 3, 4.0 g/day APR-246 will be declared the MTD.

Upon determination of the pharmacologically active dose or MTD, or when the maximally intended dose is reached, up to 10 additional patients may be enrolled at this dose level to confirm the assessment and to collect additional safety, PK and PD data to aid in determining the recommended dose of APR-246 in combination with venetoclax and rituximab.

Table 3. APR-246 Dose Levels

Dose Modification	APR-246 Dose
Dose Level 1	APR-246 1.5 g/day 0.5 g (for first 45 minutes) + 1.0 g (for 5 hours 15 minutes)
Dose Level 2	APR-246 3.0 g/day 1.0 g (for first 45 minutes) + 2.0 g (for 5 hours 15 minutes)
Dose Level 3	APR-246 4.0 g/day 1.33 g (for the first 45 minutes) + 2.66 g (for 5 hours 15 minutes)

Prior to initiation of study treatment with APR-246 administered IV in combination with venetoclax and rituximab (during treatment cycles 2-7), patients will receive APR-246 alone on Day 1 and Day 2 of the 7-day monotherapy lead-in period, during which PK and PD of APR-246 following IV and PO administration will be evaluated. On Day 1 of the monotherapy lead-in period, APR-246 will be administered IV at the assigned cohort dose. On Day 2, APR-246 will be administered PO at the dose of 500 mg. This dose may be increased based on emerging PK data to determine dose linearity after oral dosing. Patients will be required to fast for at least 10 hours prior to APR-246 PO administration. Furthermore, a sub-group of patients may receive an oral dose of APR-246 in combination with a standard high-fat meal to determine the effect of food on APR-246 absorption.

Additional dose levels may be explored if warranted based on emerging DLT, safety, PK, and/or PD data. In addition, patients who have received at least 3 cycles of therapy at the assigned dose cohort level may advance to the next higher dose level once the next higher dose level has been declared safe by the DRT.

Responses will be assessed according to response criteria for RT ([Appendix V](#)) via blood, BM, and imaging (positron emission tomography [PET]/computed tomography [CT]). Response assessments are to be performed every 3 cycles and PET-CT scanning is recommended. For patients who achieve CR, imaging may be omitted, and minimal residual disease (MRD) assessment will be completed using flow cytometry and/or molecular techniques from the BM and/or peripheral blood.

Patients may continue treatment as long as toxicity remains acceptable, the patient has not withdrawn consent and is deriving clinical benefit in the opinion of the Investigator while receiving study treatment according to the treatment durations specified for the agents in Section [4.4](#). Response and disease progression will be assessed based on the Revised Criteria for Response Assessment of Hodgkin's and Non-Hodgkin's Lymphoma (Lugano Criteria; see [Appendix V](#)), as outlined in the [Schedule of Study Evaluations](#).

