5.1.5 Recommended Dose of APR-246

The recommended dose of APR-246 in combination with venetoclax and rituximab represents the dose of APR-246 at or below the maximum intended dose, or the MTD, that results in the greatest apoptosis of circulating malignant cells in the monotherapy cycle.

The MTD of APR-246 will be defined as the dose at which <2 out of 6 patients experience DLT during the defined safety assessment period after administration of APR-246 in combination with venetoclax and rituximab. Up to 10 additional patients may be enrolled at the MTD, and at prior dose levels, to confirm the confidence at that dose level.

A DRT consisting of the Medical Monitor, Site Principal Investigators, and other clinical research personnel that the Sponsor may deem appropriate, will hold Data Review Meetings (DRMs) on an

interim basis at a frequency dependent on study accrual. At these meetings, the DRT will review any AEs, DLTs, and any available PK and PD data and make recommendations regarding the optimal dose of APR-246. All accumulated safety data will be discussed during DRMs. The optimal dose of APR-246 will be based upon the MTD and upon all accumulated safety data, PK/PD data, and preliminary efficacy data.

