8.1 Sample Size

A total of up to 48 evaluable patients will be included in the study.

Patients with RT will be enrolled and receive APR-246 at the assigned dose cohort level. Dose escalation will proceed in a 3 + 3 design. Cohorts will consist of 3-6 patients and 10 additional patients may be enrolled at the MTD. Approximately 6 + 6 + 6 (18) DLT evaluable patients will be enrolled. In the event Dose Level 3 is declared the MTD, up to 10 additional patients may be enrolled at Dose Levels 1 and 2 to gain additional safety, PK, and/or PD data to help define the recommended dose of APR-246 in this combination.

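### The escalation rule can declare an MTD on 3 patients, while Section 5.1.5 defines the MTD on 6; the two must be reconciled

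*Combined protocol and SAP*

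**What the plan says.** Section 4.1 sets out its own rules for determining the MTD, and the synopsis (Study Design) repeats them.

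- After a clean first cohort: "if there are 0 DLTs in the first 3 patients enrolled, the cohort will advance to the next level".
- After one DLT: "If there is 1 DLT in the first 3 patients enrolled to a cohort, the cohort will enroll an additional 3 patients".
- After two or more at any level above the first: "If there are ≥ 2 DLTs in a cohort, the prior lower dose level will be declared the MTD". Two or more at Dose Level 1 are referred to the Data Review Team (DRT) instead.
- At the top level, with no more than 1 DLT in the first 3: "the study will enroll 3 additional patients at Dose Level 3". That level is then the MTD if there is at most 1 DLT in the 6.

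Section 5.1.5 gives a definition: "The MTD of APR-246 will be defined as the dose at which <2 out of 6 patients experience DLT".

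Section 8.1 says "Cohorts will consist of 3-6 patients and 10 additional patients may be enrolled at the MTD", and adds that about 6 DLT-evaluable patients per level (18 in all) are expected. Section 4.1 allows, once an MTD or pharmacologically active dose is determined or the top dose is reached, that "up to 10 additional patients may be enrolled at this dose level to confirm the assessment".

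**The concern.** The declaration rule looks only at the level that failed. It asks nothing about how many patients were treated at the level below. A fill to 6 is compulsory after 1/3 at any level, and at Dose Level 3 after 0/3 as well. After 0/3 at Dose Level 1 or 2 it is not. A level cleared that way and then declared the MTD has 3 DLT-evaluable patients, yet the definition in Section 5.1.5 is written on 6.

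On this path the rule says an MTD exists and the definition says it has not been shown. That matters because the MTD caps the recommended dose (synopsis, Recommended Dose; Section 5.1.5) and its determination opens the expansion. The text does not say which prevails, so the question would be settled after the DLT data are known.

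**Working it through.** **1. The plan's own total.** Three cohorts of 6, plus 10 at the MTD, plus 10 at each of Dose Levels 1 and 2 if Dose Level 3 is the MTD: 3 × 6 + 10 + 2 × 10 = 48. This matches the stated maximum.

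**2. Where rule and definition agree or differ.**

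| Situation | Patients at declared level | Meets Section 5.1.5? |
|---|---|---|
| Prior level cleared on 1/6, next level fails | 6 | Yes |
| Dose Level 3 passes with ≤1/6 | 6 | Yes |
| Dose Level 1 has ≥2 DLTs | none declared; goes to the DRT | Not applicable |
| Dose Level 1 cleared on 0/3, Dose Level 2 fails | 3 | No |
| Dose Level 2 cleared on 0/3, Dose Level 3 fails | 3 | No |

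**3. How often the last two rows arise.** True DLT rates p1, p2, p3 at the three levels are assumptions, because the documents give none. With q = 1 − p:

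- P(cleared on 0/3) = q³
- P(cleared on 1/6) = 3pq² × q³
- P(Dose Level 2 fails) = 1 − q2³ − 3·p2·q2⁵
- P(Dose Level 3 fails) = P(≥2 DLTs in 6) = 1 − q3⁶ − 6·p3·q3⁵

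Path A = P(Level 1 on 0/3) × P(Level 2 fails). Path B = P(Level 1 cleared either way) × P(Level 2 on 0/3) × P(Level 3 fails).

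Worked case, 10/20/35%:

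- Level 1: 0.9³ = 0.7290 on 0/3, and 3 × 0.1 × 0.9⁵ = 0.1771 on 1/6; cleared in all, 0.9061.
- Level 2: 0.8³ = 0.5120 on 0/3, and 3 × 0.2 × 0.8⁵ = 0.1966 on 1/6; fails, 0.2914.
- Level 3 fails: 0.6809.
- Path A = 0.7290 × 0.2914 = 0.2124. Path B = 0.9061 × 0.5120 × 0.6809 = 0.3159. Sum = 0.5283.

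**4. How often a fill to 6 would change the answer.** A level on 0/3 fails the definition only with ≥2 DLTs in the next 3: 3p²q + p³. In the worked case this is 0.0280 at Level 1 and 0.1040 at Level 2, so 0.2124 × 0.0280 + 0.3159 × 0.1040 = 0.0388 of all trials.

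| Assumed rates, Levels 1/2/3 | Path A | Path B | MTD declared on 3 | Overturned by filling to 6 | Extra patients, 3 × path |
|---|---|---|---|---|---|
| 2/4/8% | 0.0164 | 0.0681 | 0.0845 | 0.0003 | 0.25 |
| 3/5/10% | 0.0242 | 0.0970 | 0.1212 | 0.0008 | 0.36 |
| 5/10/20% | 0.0805 | 0.2446 | 0.3250 | 0.0074 | 0.98 |
| 10/20/35% | 0.2124 | 0.3159 | 0.5283 | 0.0388 | 1.59 |
| 15/30/50% | 0.3106 | 0.2486 | 0.5592 | 0.0726 | 1.68 |

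A simulation of 400,000 trials per row agrees. Across these rows, 73% to 91% of all MTD declarations at Dose Level 1 or 2 rest on 3 patients. The figures leave out the separate stop at a pharmacologically active dose and any added dose levels.

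**5. Precision at the declared level.** Exact (Clopper–Pearson) two-sided 95% upper limits for the DLT rate are 70.8% on 0/3, 45.9% on 0/6 and 64.1% on 1/6. None excludes 33%.

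**The case against.** The strongest reply is that little turns on this. Section 4.1 is the operative procedure and gives a definite answer, and Section 5.1.5 can be read as a summary of it. Section 8.1 expects about 6 DLT-evaluable patients per level, which suggests an omitted step more than two rival designs. Up to 10 further patients may be treated at the MTD to confirm it. Stopping criteria apply throughout (Section 8.4), and Section 5.1.5 adds: "The optimal dose of APR-246 will be based upon the MTD and upon all accumulated safety data, PK/PD data, and preliminary efficacy data". The overturn figures are small, and the largest needs an assumed 50% DLT rate at Dose Level 3. An observed 0/3 also satisfies the third primary endpoint, a DLT proportion below 33%.

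Much of this stands and limits the consequence. It does not remove the conflict. The figure of 6 per level in Section 8.1 is approximate and sits beside a range of 3 to 6, so it does not bind. The expansion is optional, follows the declaration and carries no DLT rule that could revise the MTD. No text says that Section 4.1 prevails over Section 5.1.5. The protocol does not expressly give the DRT the choice between them; that it would fall to the DRT is an inference from its role in reviewing DLTs and recommending the dose.

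The cost is also slightly higher than 3 × path if an overturned Dose Level 2 leads to a second fill at a Dose Level 1 that was itself cleared on 0/3. The averages in the two highest scenarios then become 1.66 and 1.80, and a single trial could need 6 extra patients.

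**Conclusion.** The concern holds. When Dose Level 1 or 2 is cleared on 0/3 and the next level fails, the MTD declared under Section 4.1 and the synopsis does not meet the definition in Section 5.1.5. This follows from the text and does not depend on any assumed rate.

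The frequency does depend on the assumptions: 8% to 56% of trials over the rates shown. The chance that a fill to 6 would reverse the declaration is much lower, 0.03% to 7.3%. This is a gap in a core decision rule that should be fixed, with limited expected harm, because the recommended dose is selected on apoptosis at or below the cap and all safety data are reviewed.

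**What to change.** Before DLT data are seen, amend Section 4.1, the synopsis and Section 5.1.5 so that the declaration rule and the MTD definition require the same number of DLT-evaluable patients at the level declared. State what follows if the definition is not met there. Which number to use is for the sponsor to decide.

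- **If 6 is kept:** up to 3 more patients at a level, on average about 0.3 to 1.7 per trial under the assumed rates (up to 1.8 if a second fill is triggered). They fit within the planned 6 per cohort and 48 in total. Escalation takes longer, because the DLT period runs to the end of Cycle 3.
- **If the definition is aligned with cohorts of 3 to 6:** wording only, with no extra patients.
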